Appendix 11. Investigative Team Baseline Data Collection Form

Case Report Form

Patient Initials _____

Patient Study Number: _____

Date of Randomization: ____ / ____ / ____
mm dd yyyy

Time: ____ : ____ (24 hr. clock)

Enrolled by: (please print) _____

Signature: _____

Date: ____ / ____ / ____

Background Information regarding enrollment:

Subject's Contact Information:

Primary phone number: (____) ____ - ____

Secondary phone number: (____) ____ - ____

Address: _____

Street

Apt

Drug Substance: Movantik
Study Number: ESR-15-11000
Tufts IRB #12043
Version: Protocol version #19
Date: September 10, 2018

City

State

Zip

Subject's Legally Acting Representative:

Name: _____

Relationship: _____

Primary phone number: (_____) ____ - _____

Secondary phone number: (_____) ____ - _____

Address: _____

Street

Apt

_____ City _____ State _____ Zip _____

initials of investigational team member completing/verifying form _____ date _____

Drug Substance: Movantik
Study Number: ESR-15-11000
Tufts IRB #12043
Version: Protocol version #19
Date: September 10, 2018

Baseline Characteristics

Pt Number _____	Patient Initials _____	Date _____ / _____ / _____
-----------------	------------------------	----------------------------

1. Date of Birth: _____ / _____ / _____

2. Age: _____ years

3. Gender: M F

4. Height: _____ inches

5. Weight: _____ kg

6. Hospital admission date: (to study hospital) _____ / _____ / _____

7. ICU admission date: (in study hospital) _____ / _____ / _____

8. Location prior to hospitalization (includes hospitalization at Tufts Medical Center and any outside hospital)

 Home alone	 Senior housing (w/ minimal assisted living)
 Home with a spouse	 Assisted living facility
 Home with other family member/friends	 Long term care facility
 Rehabilitation	 Other: _____

9. Location immediately prior to this ICU admission:

 Tufts emergency department	 ICU at outside hospital, admit date: _____ / _____ / _____
 Tufts hospital ward	 Ward at outside hospital, admit date: _____ / _____ / _____
 Tufts operating room following elective surgery	 Other: _____
 Tufts operating room following emergency surgery	

Drug Substance: Movantik
Study Number: ESR-15-11000
Tufts IRB #12043
Version: Protocol version #19
Date: September 10, 2018

10. Prior ICU stay during this hospital admission: Yes No

If YES, specify unit: _____

11. Was a tracheotomy present on admission to ICU? Yes No

If YES, was it performed during this hospital admission? Yes No

12. Start date of mechanical ventilation: Date: ____/____/____ Time: ____:____ (24hr clock)

13. Admission APACHE III Diagnosis Code (Please see attached): _____

If "other" has been selected in any category, please specify: _____

14. APACHE II Score (Please see attached): Calculate APACHE II score using values from the 24 hour period prior to randomization.

APS: _____

Age Points: _____

Chronic Health Points: _____

Total APACHE II: _____

initials of investigational team member completing/verifying form _____ date _____

Drug Substance: Movantik
 Study Number: ESR-15-11000
 Tufts IRB #12043
 Version: Protocol version #19
 Date: September 10, 2018

Pt Number	Patient Initials	Date
____ / ____ / ____	____ - ____ - ____	

15. Baseline SOFA Score (Please see attached): Calculate SOFA score using values from the 24 hour period prior to randomization.

Total SOFA: ____

16. Last Spontaneous Bowel Movement (Per medical record review/family interview):

Date: ____ / ____ / ____

Time: ____ : ____ (24 hour clock)

17. Current infusions at randomization: (check all that apply)

Fentanyl:	 Yes	 No	Start date: ____ / ____ / ____	Time: ____ : ____	Rate: ____ mcg/hr
Hydromorphone:	 Yes	 No	Start date: ____ / ____ / ____	Time: ____ : ____	Rate: ____ mg/hr
Morphine:	 Yes	 No	Start date: ____ / ____ / ____	Time: ____ : ____	Rate: ____ mg/hr
Midazolam:	 Yes	 No	Start date: ____ / ____ / ____	Time: ____ : ____	Rate: ____ mg/hr
Lorazepam:	 Yes	 No	Start date: ____ / ____ / ____	Time: ____ : ____	Rate: ____ mg/hr
Propofol:	 Yes	 No	Start date: ____ / ____ / ____	Time: ____ : ____	Rate: ____ mcg/kg/min
Dexmedetomidine:	 Yes	 No	Start date: ____ / ____ / ____	Time: ____ : ____	Rate: ____ mcg/kg/hr
Other: _____			Start date: ____ / ____ / ____	Time: ____ : ____	Rate: ____ /hr

18. Opioid Medications at randomization: (check all that apply)

Fentanyl:	 Yes	 No	Start date: ____ / ____ / ____	Dose in last 24 hours ____ mcg
Hydromorphone:	 Yes	 No	Start date: ____ / ____ / ____	Dose in last 24 hours ____ mg
Morphine:	 Yes	 No	Start date: ____ / ____ / ____	Dose in last 24 hours ____ mg

Drug Substance: Movantik
Study Number: ESR-15-11000
Tufts IRB #12043
Version: Protocol version #19
Date: September 10, 2018

Oxycodone: Yes No Start date: ____/____/_____ Dose in last 24 hours ____ mg
Hydrocodone: Yes No Start date: ____/____/_____ Dose in last 24 hours ____ mg
Methadone: Yes No Start date: ____/____/_____ Dose in last 24 hours ____ mg
Other: _____ Start date: ____/____/_____ Dose in last 24 hours ____ mg

19. Reason for Opioid Initiation: (check all that apply)

- Analgesia for Mechanical Ventilation
- Postoperative Pain
- Cancer Pain
- Periprocedural Pain
- Wound Care

initials of investigational team member completing/verifying form _____ **date** _____

Baseline APACHE II Calculator

Pt Study ID: Pt Initials:

Please retain this worksheet at the site with the CRF.

Calculate APACHE II score using values from the 24 hour period prior to randomization.

Please circle appropriate range on form

A. Physiologic Variables Points

PHYSIOLOGIC VARIABLE	HIGH ABNORMAL RANGE					LOW ABNORMAL RANGE				PT SCORE
	4	3	2	1	0	1	2	3	4	
Temperature -core (°C)	≥ 41	39-40.9		38.5-38.9	36-38.4	34-35.9	32-33.9	30-31.9	≤ 29.9	
MAP (mmHg)	≥ 160	130-159	110-129		70-109		50-69		≤ 49	
Heart Rate	≥ 180	140-179	110-139		70-109		55-69	40-54	≤ 39	
Respiratory Rate (non-ventilated or ventilated)	≥ 50	35-49		25-34	12-24	10-11	6-9		≤ 5	
Oxygenation: [A-aDO ₂ = (FiO ₂ x 710) - (PCO ₂ x 1.25) - PO ₂]				FiO ₂ =	PCO ₂ =	PO ₂ =				

Drug Substance: Movantik
 Study Number: ESR-15-11000
 Tufts IRB #12043
 Version: Protocol version #19
 Date: September 10, 2018

a. If $\text{FiO}_2 \geq 0.5$ record A-aDO ₂	≥ 500	350-499	200-349		< 200					
b. If $\text{FiO}_2 < 0.5$ record only PaO ₂					PO ₂ > 70	PO ₂ 61-70		PO ₂ 55-60	PO ₂ < 55	
Arterial pH	> 7.7	7.6-7.69		7.5-7.59	7.33-7.49		7.25-7.32	7.15-7.24	< 7.15	
Serum Na (mEq/L)	≥ 180	160-179	155-159	150-154	130-149		120-129	111-119	≤ 110	
Serum K (mEq/L)	≥ 7	6-6.9		5.5-5.9	3.5-5.4	3-3.4	2.5-2.9		< 2.5	
**Serum Creatinine ** (mg/dL)	> 3.5	2-3.4	1.5-1.9		0.6-1.4		<0.6			
Hematocrit (%)	≥ 60		50-59.9	46-49.9	30-45.9		20-29.9		< 20	
WBC ($10^3/\mu\text{L}$)	≥ 40		20-39.9	15-19.9	3-14.9		1-2.9		< 1	
Glasgow Coma Score (GCS)	Score = 15 minus actual GCS (see below)									
Serum HCO ₃ (venous mEq/L) - not preferred, use only if no ABG's	≥ 52	41-51.9		32-40.9	22-31.9		18-21.9	15-17.0	< 15	
ACUTE PHYSIOLOGY SCORE (APS): Sum of the 12 individual variables										
** Acute Renal Failure – double the creatinine points for ARF (cr > 2.5 mg/dL in a subject with prior normal kidney function)										

B. Age Points - Assign points to age as follows:

AGE (yrs)	POINTS
≤ 44	0
45-54	2
55-64	3
65-74	5
≥ 75	6

AGE SCORE =

C. Chronic Health Points - If the patient has a history of :

severe organ insufficiency or is immunocompromised assign points as follows:

- For nonoperative or emergency postoperative pt -- 5 points
- For elective postoperative pt -- 2 points

CHRONIC HEALTH SCORE

D. APACHE II SCORE - Sum of A + B + C

A. APS points	
B. Age points	
C. Chronic Health points	

GLASCO COMA SCALE		
1) Parameter	2) Response	Points Assigned (please circle)
Eyes Open	Spontaneously	4
	On spoken command	3
	On pain	2
	No response	1
Best Motor Response	To spoken command	6
	To painful stimulus:	
	Localized pain	5
	Flexion withdrawal	4
	Flexion abnormal	3
	Extension	2
Best Verbal Response	No response	1
	(Not on ventilator)	
	Oriented & converses	5
	Disoriented & converses	4
	Inappropriate words	3
	Incomprehensible sounds	2
	No response	1
	(On ventilator)	
	Appears oriented	5
	Questionably oriented	3
	Generally unresponsive	1

Drug Substance: Movantik
Study Number: ESR-15-11000
Tufts IRB #12043
Version: Protocol version #19
Date: September 10, 2018

APACHE II SCORE =

CHRONIC HEALTH DEFINITIONS *Please check all that apply*

Organ insufficiency or immuno-compromised state evident prior to this hospital admission and conform to the following criteria:

- LIVER:** Biopsy proven cirrhosis and documented portal hypertension; episodes of past upper GI bleeding attributed to portal hypertension; or prior episodes of hepatic failure/encephalopathy/coma
- CARDIOVASCULAR:** New York Heart Association Class IV
- RESPIRATORY:** Chronic restrictive, obstructive, or vascular disease resulting in severe exercise restriction i.e. unable to climb stairs or perform household duties; or documented chronic hypoxia, hypercapnia, secondary polycythemia, severe pulmonary hypertension (>40 mmHg), or respirator dependency
- RENAL:** Receiving chronic dialysis
- IMMUNO-COMPROMISED:** The patient has received therapy that suppresses resistance to infection i.e. Immuno-suppression, chemotherapy, radiation, long term or recent high dose steroids, or has a disease that is sufficiently advanced to suppress resistance to infection (i.e. leukemia, lymphoma, AIDS)

initials of investigational team member completing/verifying form _____ **date** _____

Baseline SOFA Calculator

Pt Study ID: Pt Initials:

Please retain this worksheet at the site with the CRF.

Calculate SOFA score using values from the 24 hour period prior to randomization

A. Please circle appropriate score

Drug Substance: Movantik
 Study Number: ESR-15-11000
 Tufts IRB #12043
 Version: Protocol version #19
 Date: September 10, 2018

Organ System	0	1	2	3	4	Score
RESPIRATION PaO ₂ /FiO ₂ (mmHg)	>400	301-400	201-300	101-200 with respiratory support	< 100 with respiratory support	
CARDIOVASCULAR Vasopressors (mcg/kg/min)	No hypotension	MAP < 70mmHg and No vasopressors	Dopamine ≤ 5 or Any dose Dobutamine	Dopamine > 5 or Epinephrine ≤ 0.1 or Norepinephrine ≤ 0.1	Dopamine >15 or Epinephrine > 0.1 or Norepinephrine > 0.1 or any dose Vasopressin	
LIVER (bilirubin) (mg/dl)	<1.2	1.2 – 1.9	2.0 – 5.9	6.0 – 11.9	≥ 12	
COAGULATION Platelets (x 10 ³ /µL)	>150	101-150	51-100	21-50	≤20	
RENAL Creatinine (mg/dL) or urine output mL/hr	<1.2	1.2 - 1.9	2.0 -3.4	3.5 – 4.9 or < 500 ml/day	≥ 5.0 or < 200 ml/day	
TOTAL SOFA=						

B. Please record below the actual values used in the scoring above.

PaO₂ |__|__|__|

Drug Substance: Movantik
Study Number: ESR-15-11000
Tufts IRB #12043
Version: Protocol version #19
Date: September 10, 2018

FiO₂ | | . | | |

MAP | | | |

Bilirubin | | | | μmol/L

Platelets | | | | x 10³/μL

Creatinine | | | | μmol/L or Urine output | | | | | mL/day

initials of investigational team member completing/verifying form _____ **date** _____

12. STATISTICAL METHODS AND SAMPLE SIZE DETERMINATION

12.1 Description of analysis sets

All patients will be analyzed in the groups to which they were randomly assigned, according to the intention-to-treat principle.

12.2 Methods of statistical analysis

[figure not shown]
Baseline characteristics of patients will be compared using standard univariate methods (chi-square test, t-test) to confirm the randomization was successful in achieving comparable groups. To test the primary outcome (incidence of lower GI tract paralysis), given that there may be censoring (i.e., subject may die or withdraw from study before developing lower GI tract paralysis), we will present Kaplan-Meier curves for the naloxegol and placebo groups for the time to first development of lower GI tract paralysis (≥ 3 days without a SBM after study randomization) during the ICU stay up to 10 days and compare the curves using a log-rank test. If all subjects complete the study (e.g., no deaths, no withdrawal or loss-to-follow-up for other reasons), then we will instead compare the proportion of patients that develop lower GI tract paralysis after study randomization during the ICU stay up to 10 days between the naloxegol and placebo groups using a chi-square test. The secondary outcome, time to first SBM will be estimated using a Kaplan Meier time to event analysis and compared between groups using a log-rank test. The secondary outcome of the number of ICU days without a SBM will be compared between the naloxegol and placebo groups using the Poisson regression for count data and adjusting for total number of days in the ICU (up to a maximum of 10) as an offset term in the Poisson model. The secondary outcome of the average daily opioid requirements will be compared between groups using either a student t-test or nonparametric Wilcoxon rank-sum test if the assumptions of the student t-test fail to be met. Length of mechanical ventilation and ICU stay will be reported as medians and interquartile ranges and will be compared using the Wilcoxon Rank Sum Test. For all statistical tests of hypotheses, a two-sided p-value of ≤ 0.05 will be considered as statistically significant. As this is a Phase II proof of concept study a p value of <0.10 may still be worth consideration for future study, however. All statistical analyses will be performed using SPSS 17.0. (SPSS, Chicago, IL) or other comparable commercially available statistical software.

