 - b. Presence of coma (SAS = 1 or 2)
- n. Daily presence of delirium using the Intensive Care Delirium Screening Checklist (ICDSC)
 - a. Proportion of patients ever found with delirium (ICDSC \geq 4]
 - b. Days with delirium
 - c. Proportion of patients ever found with subsyndromal delirium [ICSDC = 1 to 3]
 - d. Days with subsyndromal delirium
- o. Daily total sedation administered (in midazolam equivalents)
- p. Occurrence of lower GI tract paralysis requiring consultation by a gastroenterologist or a surgeon.
- q. Days without mechanical ventilation support.
- r. Duration of ICU stay.
- s. In patients having a clinical reason for foley catheter placement, abdominal pressure measurement every 8 hours:
 - i) % patient of patients having abdominal pressure \geq 12 mmHg; ii) % patient of patients having abdominal pressure \geq 20 mmHg; iii) Average daily maximal abdominal pressure score
- t. Time from first initiation of \geq 100 fentanyl equivalents to administration of first dose of study medication.

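### Baseline significance tests on 18 patients per arm cannot confirm comparability, and neither time-to-event analysis is adjusted for hours since the last bowel movement, which Appendix 11 allows to be derived

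*SAP*

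**What the plan says.** SAP 12.2 (the same text is in Protocol 12.2) states: "Baseline characteristics of patients will be compared using standard univariate methods (chi-square test, t-test) to confirm the randomization was successful in achieving comparable groups". It does not say what follows from either result.

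For the primary outcome, time from randomisation to first paralysis, the SAP will present Kaplan-Meier curves "during the ICU stay up to 10 days and compare the curves using a log-rank test". If every subject completes, a chi-square test of proportions replaces this. The first bowel movement, a secondary outcome, is handled likewise: "time to first SBM will be estimated using a Kaplan Meier time to event analysis and compared between groups using a log-rank test". Neither analysis names a covariate or stratum. The only adjustment in the section is "adjusting for total number of days in the ICU (up to a maximum of 10) as an offset term in the Poisson model", which accounts for length of observation and not for prognosis.

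Randomisation is in blocks of 4 with no stratification factor stated (Protocol 5.2.2). Appendix 11 records the date and clock time of randomisation and, as an item with its own date and time, "16. Last Spontaneous Bowel Movement (Per medical record review/family interview". Hours since last SBM at randomisation can therefore be derived, but no planned analysis uses them.

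**The concern.** Under randomisation a significant baseline difference is a chance finding, and in a trial of 36 a non-significant one says little about how alike the arms are. A reader told that comparability was confirmed would be falsely reassured.

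The covariate left out is a plausible predictor. Patients may enter up to 72 hours after opioid start, so they are randomised at different points of a stool-free interval, while the primary clock starts at randomisation. The laxative guideline (Appendix 1) counts days without stool from opioid initiation, so the interval before randomisation also affects when laxative steps begin inside the outcome window. If one arm by chance had gone longer without stool, the unadjusted comparison would carry that imbalance and the planned check would often miss it. Protocol 1.2 says the trial should inform how confounders are identified and managed in later studies; SAP 12.2 does not take this up.

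**Working it through.** **Inputs.** From the documents: 18 per arm, two-sided alpha 0.05, proportions without SBM at day 4 of 90% vs 40%, 80% vs 50% and 70% vs 40% (SAP 12.2.2), and follow-up to 10 days (SAP 12.2). Assumed, because the documents give nothing: a standard normal covariate with a log-linear effect, hazard ratio (HR) per SD of 1.0, 1.5, 2.0 or 3.0.

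**1. The plan's own power.** Take constant hazards, HR = ln(S1)/ln(S2), events = 18 × (2 − S1^2.5 − S2^2.5) and power = Φ(√events/2 × |ln HR| − 1.96). For 90% vs 40%:
- HR = 0.105/0.916 = 0.115
- events = 18 × (2 − 0.768 − 0.101) = 20.3
- power = Φ(2.26 × 2.16 − 1.96) = Φ(2.92) = 99.8%, as stated

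The next three columns give 98.4%, 93.2% and 76.7%, against 98.4%, 92.7% and 76.0% stated. For 70% vs 40% the method gives 68.5%, not the stated 76.0%. That column repeats the 80% vs 50% column in every row, which is a separate matter.

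**2. What the baseline check can detect.** The standard error of a standardised difference is √(2/18) = 0.333.
- Chance of an imbalance above 0.5 SD in a given covariate: P(|Z| > 0.5/0.333 = 1.5) = 13.4%.
- Difference needed for p<0.05 with 34 degrees of freedom: 2.03 × 0.333 = 0.68 SD.
- Power for a 0.5 SD difference (noncentrality 1.5): about 31%.
- The chance of exceeding 0.67 SD is 4.4%. So in about 13.4 − 4.4 = 9% of trials the imbalance lies between 0.5 SD and the threshold, and the check would pass it.

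None of these figures depends on the covariate's prognostic strength.

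**3. False-positive rate.** I simulated the plan's exponential model under no treatment effect (both arms at 80%, then both at 60%), with 3,000 replicates each. Over all trials the unadjusted log-rank test rejected in 4.9% to 6.2%. Within the roughly 13% of trials with imbalance above 0.5 SD:

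| HR per SD | Unadjusted log-rank | Cox adjusted |
|---|---|---|
| 1.0 | 3.0%, 5.0% | 3.2%, 6.2% |
| 1.5 | 8.4%, 4.8% | 7.0%, 4.5% |
| 2.0 | 10.3%, 13.5% | 6.8%, 5.2% |
| 3.0 | 16.3%, 19.9% | 6.3%, 5.1% |

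Each cell rests on about 400 trials, so its simulation error is about √(0.05 × 0.95/400) = 1.1 points at a 5% rate.

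**4. Power, unadjusted log-rank to adjusted Cox.** The same model was used. Its event is defecation, so it represents time to first SBM.

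| HR per SD | 90% vs 40% | 80% vs 50% | 70% vs 40% |
|---|---|---|---|
| 1.0 | 99.8 → 99.7% | 75.4 → 74.5% | 67.8 → 67.2% |
| 1.5 | 99.6 → 99.7% | 73.8 → 77.4% | 64.8 → 70.1% |
| 2.0 | 98.9 → 99.9% | 68.4 → 81.0% | 62.0 → 76.7% |
| 3.0 | 97.7 → 99.9% | 63.0 → 85.7% | 56.5 → 83.8% |

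The gain in the two weaker scenarios runs from 77.4 − 73.8 = 3.6 to 83.8 − 56.5 = 27.3 points. In the headline scenario it is at most 99.9 − 97.7 = 2.2. With a covariate that predicts nothing, the loss is at most 75.4 − 74.5 = 0.9.

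**5. Paralysis itself.** A separate simulation treated bowel movements as a renewal process. It assumed a 72-hour no-SBM probability of 0.70 vs 0.40 and ICU censoring uniform on 2 to 14 days, capped at 10. For rate effects of 1.5-, 2.0- and 2.7-fold per SD, adjustment changed power for paralysis by −1 to +3 points (500 replicates). In trials with imbalance above 0.5 SD, the unadjusted false-positive rate for paralysis was 8%, 12% and 17% (2,000 replicates).

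**6. An imprecise covariate.** With an assumed reliability of 0.5 and HR 2.0 per SD, power moved from 70.6% to 74.1% (80% vs 50%) and from 62.4% to 66.7% (70% vs 40%). At HR 1.5 the gain was about 2 points; for 90% vs 40% it was about 0.

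**The case against.** The best defence is that an unadjusted log-rank test is a legitimate choice in a small proof-of-concept trial. Its overall error rate is near nominal, and the baseline tests alter no inference because nothing depends on them. That stands.

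A reader might infer that the missing adjustment costs power in both time-to-event analyses. The documents do not support that. They give no estimate of how strongly hours since last SBM predicts anything, the change for paralysis is −1 to +3 points, and in the plan's headline scenario at most about 2 points can be gained. Nor does a conditional false-positive rate of up to 20% make the test invalid: it applies only to the roughly 13% of trials with a marked imbalance, and only under the assumed effects.

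The covariate also has limits. It comes from records or family interview and may be imprecise or missing. Excluding patients with existing paralysis or scheduled laxative use may narrow its range. Because laxative steps are timed from opioid start, patients randomised late reach them sooner after randomisation, so the effect need not be log-linear or even monotone. These points reduce the likely gain, but they do not rescue the baseline tests or remove the value of one pre-specified adjusted analysis.

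Finally, Protocol 2.2(t), the time from first reaching 100 "fentanyl equivalents to administration of first dose of study medication", may look like a baseline covariate misfiled as an efficacy outcome. It ends at first dose, after randomisation, and SAP 12.2 specifies no test for it. That is a question of list placement, and no consequence for the analysis has been shown.

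**Conclusion.** The point holds in limited form. That the baseline tests cannot confirm comparability follows from the sample size alone. That a chance imbalance in hours since last SBM would go uncorrected follows from the text of SAP 12.2.

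How much this matters depends on a prognostic strength that has to be assumed. At HR 1.5 to 3 per SD, the false-positive rate in trials with imbalance above 0.5 SD is roughly 5% to 20% unadjusted, against about 5% to 7% adjusted. For time to first SBM, adjustment adds about 4 to 27 points of power in the 80% vs 50% and 70% vs 40% scenarios, and less if the time is poorly recorded. For paralysis the benefit is protection against imbalance rather than power. The planned log-rank test remains valid.

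**What to change.** In SAP 12.2 and Protocol 12.2:

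1. Remove the baseline tests and show baseline characteristics descriptively by arm, including hours since last SBM.
2. For time to first SBM measured from randomisation (Protocol 2.2, item e), pre-specify a Cox model with arm and hours since last SBM at randomisation. Use a form defined at zero, such as log(hours + 1), a likelihood-ratio test, and Efron or exact handling of ties.
3. For time to paralysis, keep the log-rank test and report the same Cox model beside it as a pre-specified adjusted analysis.
4. If all subjects complete and the chi-square test applies, report a matching adjusted comparison, for example logistic regression with arm and the same covariate.
5. State a rule for missing times that does not use treatment arm, such as the pooled median. Fix the covariate's functional form before unblinding, and note that laxative timing may make its effect non-monotone.

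The cost is wording and one covariate, with no new data. The downside is about 1 point of power if the covariate is not prognostic, and a smaller gain if it is imprecisely recorded.

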
Overall Study Aim

The overall aim of this Phase II, proof of concept study is to evaluate the efficacy and safety of naloxegol (versus placebo) in preventing lower GI tract paralysis in critically ill adults initiated on scheduled intravenous (IV) opioid therapy.

2. 1 Primary objective

The primary objective of this single-center, Phase II, proof of concept study in critically ill adults initiated on scheduled IV opioid therapy is to compare the incidence of lower GI tract paralysis [from the time of a study enrollment (i.e., randomization) to ICU discharge, death or 10 days of study drug administration (whichever comes first)] between naloxegol 25mg daily and placebo-treated groups.

Drug Substance: Movantik
 Study Number: ESR-15-11000
 Tufts IRB #12043
 Version: Protocol version #19
 Date: September 10, 2018

Note:

1. For the purposes of the study, any rectal output will be considered a SBM as long as it is not temporally related to the insertion of a rectal tube or the insertion of a suppository (as per the study laxative protocol (Appendix 1)).
2. Patients with preexisting lower GI tract paralysis are excluded from the study.
3. Patients not expected to survive their ICU stay are excluded from the study.

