12.2 Methods of statistical analysis

Baseline characteristics of patients will be compared using standard univariate methods (chi-square test, t-test) to confirm the randomization was successful in achieving comparable groups. To test the primary outcome (incidence of lower GI tract paralysis), given that there may be censoring (i.e., subject may die or withdraw from study before developing lower GI tract paralysis), we will present Kaplan-Meier curves for the naloxegol and placebo groups for the time to first development of lower GI tract paralysis (≥ 3 days without a SBM after study randomization) during the ICU stay up to 10 days and compare the curves using a log-rank test. If all subjects complete the study (e.g., no deaths, no withdrawal or loss-to-follow-up for other reasons), then we will instead compare the proportion of patients that develop lower GI tract paralysis after study randomization during the ICU stay up to 10 days between the naloxegol and placebo groups using a chi-square test. The secondary outcome, time to first SBM will be estimated using a Kaplan Meier time to event analysis and compared between groups using a log-rank test. The secondary outcome of the number of ICU days without a SBM will be compared between the naloxegol and placebo groups using the Poisson regression for count data and adjusting for total number of days in the ICU (up to a maximum of 10) as an offset term in the Poisson model. The secondary outcome of the average daily opioid requirements will be compared between groups using either a student t-test or nonparametric Wilcoxon rank-sum test if the assumptions of the student t-test fail to be met. Length of mechanical ventilation and ICU stay will be reported as medians and interquartile ranges and will be compared using the Wilcoxon Rank Sum Test. For all statistical tests of hypotheses, a two-sided p-value of ≤ 0.05 will be considered as statistically significant. As this is a Phase II proof of concept study a p value of <0.10 may still be worth consideration for future study, however. All statistical analyses will be performed using SPSS 17.0. (SPSS, Chicago, IL) or other comparable commercially available statistical software.

[figure not shown]

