12.2.2 Determination of sample size

For the power analysis, the 4-day estimates of failure to defecate (i.e., failure to have a SBM) from the Kaplan-Meier plot presented in the Guardiola et. al. paper [4] was used as the estimate of lower GI tract paralysis. The figure below shows that the estimate of the percent of patients who failed to defecate (1 minus plotted proportion with defecation) by day 4 was 40% in the Prophylaxis group (i.e., the intervention group) vs. 90% in the non-prophylaxis (Treatment) group (i.e., the control group) (see yellow highlights in figure). We believe the 4-day estimate will be strongly related to the primary outcome of lower GI tract paralysis (≥ 3 days without a SBM).

90% (Placebo) vs. 40% (Prophylactic treatment), all subjects have complete follow-up, and the analysis is done using the log-rank test to compare survival curves. As sensitivity analysis, the table also shows the power of the study with this sample size under different scenarios. Because this is not the final definitive study to determine efficacy, a less stringent alpha of 0.10 may be justified for this Phase II proof-of-concept study which, if positive, would be followed by a confirmatory study [15]. While we expect most subjects to finish the study (based on the inclusion criteria), we have shown the impact on the power if approximately 20% of subjects do not finish the study. We have also varied the estimated proportion of patients failing to defecate by day 4 (i.e., not having a SBM) in the placebo group from 90% to 70% and in the prophylactic treated group from 40% to 50%.

Statistical Power of Log-Rank Test with n=18 subjects per group (36 total)

Complete study	ALPHA	Proportion Failing to Defecate at Day 4 (Placebo vs. Prophylactic Treated)				
		90% vs. 40%	90% vs. 50%	80% vs. 40%	80% vs. 50%	70% vs. 40%
100%	0.05	99.8%	98.4%	92.7%	76.0%	76.0%
	0.10	100.0%	99.4%	96.2%	84.9%	84.9%
80%	0.05	99.7%	97.6%	90.8%	72.5%	72.5%
	0.10	99.9%	99.0%	95.1%	82.2%	82.2%

For this Naloxogol randomized trial, we propose enrolling 36 subjects, 18 per group. The statistical power table below shows this sample size yields over 95% power using an alpha of 0.05 if the true day 4 estimated freedom of event (defecation) rates are

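### The Kaplan-Meier display of the primary outcome treats death as censoring and leaves ICU discharge unaddressed, so it would sit at or above the in-ICU incidence that the objective asks for

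*SAP*

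**What the plan says.** Protocol 2.1 makes the primary outcome an incidence, counted from randomization "to ICU discharge, death or 10 days of study drug administration (whichever comes first". Three things can close the window: discharge, death, or the end of ten days of study drug.

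SAP 12.2 (Protocol 12.2 has the same text) analyses the outcome as time to first paralysis, "given that there may be censoring (i.e., subject may die or withdraw from study before developing lower GI tract paralysis". It presents Kaplan-Meier curves over the ICU stay up to 10 days and compares them by log-rank test. If every subject completes, with no death, withdrawal or other loss, it switches to a chi-square test of simple proportions. ICU discharge appears neither as a reason for censoring nor among the things that stop a subject from completing. No competing-risk method is mentioned, and no numerical incidence estimate is specified for the Kaplan-Meier route.

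**The concern.** A patient who dies can no longer develop paralysis, and under Protocol 2.1 a patient who is discharged has left the outcome window. For an incidence defined this way, both are competing events rather than incomplete follow-up. Kaplan-Meier censoring treats such a patient as still at risk, with the same hazard as those who remain. It therefore estimates the incidence that would occur if nobody died or left, which is not the quantity in the objective.

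The two planned routes also aim at different quantities. The chi-square route uses simple proportions, which is the in-ICU incidence. The Kaplan-Meier route does not, and whether anyone dies or withdraws decides which one is used.

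What is at stake is the estimate. Protocol 1.2 says that effect size and variability are unknown and that this trial should inform the sample size and outcomes of larger ones. The investigators took their own planning figures from a published Kaplan-Meier plot (SAP 12.2.2), so a later team could well use these curves in the same way.

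**Working it through.** **Plan's own figure.** The plan has no incidence or exit-rate calculation to reproduce. The nearest figure is the power: "we propose enrolling 36 subjects, 18 per group", and "this sample size yields over 95% power using an alpha of 0.05" (table entry 99.8%), with failure to defecate "by day 4 was 40% in the Prophylaxis group (i.e., the intervention group) vs. 90% in the non-prophylaxis (Treatment) group". With exponential time to first defecation and follow-up to day 10:

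- HR = ln(0.9)/ln(0.4) = 0.115, so |ln HR| = 2.163.
- Expected events = 18 × [(1 − 0.9^2.5) + (1 − 0.4^2.5)] = 18 × (0.232 + 0.899) = 20.3.
- Power = Φ(2.163 × √20.3 / 2 − 1.96) = Φ(2.92) = 99.8%.

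The figure reproduces. The table's 80% rows also reproduce (apart from the 70% vs 40% column) if 20% are lost exponentially over 10 days, so that reading of the plan's non-completion figure is used below.

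**Constant-hazard check.** Let h be the daily hazard of paralysis and l the daily hazard of death plus discharge. Let x be the share who would leave by day 10 if paralysis never occurred.

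- 1-KM at day 10 = 1 − exp(−10h)
- In-ICU incidence = h/(h+l) × [1 − exp(−10(h+l))]

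The documents do not give x, so it is an assumed range. The 1-KM levels tried are 90% and 40% (the planning figures, used only as levels) and 72% (the upper background figure in Protocol 1.1). Worked example for 72% and x = 20%: h = −ln(0.28)/10 = 0.1273 and l = −ln(0.80)/10 = 0.0223. The in-ICU incidence is 0.1273/0.1496 × (1 − 0.28 × 0.80) = 0.851 × 0.776 = 66.0%.

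| 1-KM | x = 5% | 10% | 20% | 50% | 70% |
|---|---|---|---|---|---|
| 90% | 88.5 | 87.0 | 83.9 | 73.0 | 63.7 |
| 72% | 70.6 | 69.1 | 66.0 | 55.7 | 47.1 |
| 40% | 39.1 | 38.1 | 36.2 | 29.7 | 24.4 |

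The overstatement is about 1 to 3 points at 5 to 10% exits, 4 to 6 at 20%, and 10 to 26 at 50 to 70%.

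**Check with the event as defined.** Bowel movements were simulated at constant rates matched to the day-4 figures: −ln(0.9)/4 = 0.0263 and −ln(0.4)/4 = 0.2291 per day. The event is the first 3-day gap. With 20% exits by day 10, 1-KM is 100% and 97.5% against in-ICU incidences of 93.3% and 89.1%, an overstatement of about 7 and 8 points. If the rate after the first movement is instead 1 per day, 1-KM is about 95% and 66%, and the overstatement is about 6 and 5 points. Across these models, 20% exits give about 4 to 9 points.

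**Timing.** The event cannot occur before day 3, so early exits cost most. If most paralysis occurs at day 3 and 20% have already left by then, 72% becomes 0.72 × 0.80 = 57.6%. That is a heavier exit pattern than 20% spread over 10 days.

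**The test.** With equal paralysis hazards (72% in each arm) and exits of 30% vs 70%, the simulated log-rank test rejected in 5.9% of trials, against 5.6% with equal exits of 50%. The chi-square test of simple proportions rejected in 18.6%, because the in-ICU proportions then truly differ (62.6% vs 47.2%). This shows that the two routes answer different questions, not that the log-rank test fails.

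**The case against.** Four objections have weight.

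*Discharge is not named.* A reader might infer that the plan censors ICU discharge. SAP 12.2 names only death and withdrawal. Carrying discharged patients event-free to day 10 also fits the text, and discharge would then cause no overstatement. This stands: what can be shown is that discharge handling is unspecified. Because observation ends at discharge, censoring is still the likely default, and the gap needs filling.

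*No percentage is said to be read from the curves.* True. The SAP presents and tests them, and simple counts are not ruled out. But the curves are the only planned display of an outcome called incidence whenever anyone dies or withdraws.

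*The primary inference is sound.* True, and conceded. A reader might infer that the p-value is compromised. The simulations above do not support that.

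*The effect is small beside sampling error.* With 18 per arm, an incidence of 40% has a 95% half-width of about 1.96 × √(0.4 × 0.6/18) = 23 points. Death alone may also add little, since a note in Protocol 2.1 excludes patients not expected to survive the ICU stay, although exclusion criterion r in Protocol 4.2 uses a 24-hour limit. This keeps the point modest. The bias nevertheless has a known direction and costs almost nothing to remove.

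**Conclusion.** The point holds as a mismatch between the stated outcome and its planned display. Death is censored by the text, discharge is left open, and 1-KM is at or above the in-ICU incidence. The likely size is about 1 to 3 points at 5 to 10% exits and about 4 to 9 points at about 20%, with exits spread over the 10 days. The 20% is the plan's own non-completion figure, which may not count discharge. An overstatement of 10 points to several tens needs common exits, which in practice means that discharge is frequent and is censored.

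A reader might go further and expect a near-100% incidence overstated by 14 to 52 points. The documents do not support this. The near-100% level comes from assuming a constant bowel-movement rate for 10 days, and it appears with no exits at all (100% and 97.5%). The 14 to 52 points need exits of 5 to 20% per day, or 39 to 86% gone by day 10, and no such rate is given. The change is worth making for the estimate. It is not a threat to the primary test.

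**What to change.** In SAP 12.2 and Protocol 12.2:

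- State how ICU discharge is handled, and name death and alive ICU discharge as competing events for the primary outcome.
- Present Aalen-Johansen cumulative incidence curves in place of Kaplan-Meier curves for this outcome. Report day-10 incidence per arm and the difference, with confidence intervals.
- Show the cumulative incidence of death and of discharge per arm alongside, so that a difference in exits is not mistaken for an effect on paralysis.
- Keep the log-rank test, described as a comparison of cause-specific hazards.

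With no other loss, the Aalen-Johansen estimate equals the simple proportion, so the two routes would then estimate the same incidence. The cost is a change of SAP wording and slightly more analysis work with standard software. No new data, no change to the primary test and no change in sample size are needed. The reported incidences will be lower than 1-KM would show.
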